### 3 Background information and rationale for the trial

The trial will be conducted in compliance with this protocol, ICH GCP and applicable regulatory requirements, and in accordance with the Declaration of Helsinki.

In this document, the term investigator refers to the individual responsible for the overall conduct of the clinical trial at a trial site.

#### 3.1 Background information

##### Prader Willi syndrome

Prader-Willi syndrome (PWS) is a genetic disorder characterised by hypotonia with poor sucking reflex, feeding difficulties, and poor weight gain during infancy, hypogonadism, growth hormone insufficiency causing short stature, mild to moderate mental retardation, early childhood-onset hyperphagia and obesity. Birth incidence has been estimated at around 1: 30,000 and population prevalence at about 1: 50,000^6.

Obesity typically manifests in early childhood and is a major cause of morbidity and mortality and is strongly associated with multiple comorbid conditions, including cardiopulmonary compromise, type 2 diabetes mellitus (T2DM), hypertension, thrombophlebitis, chronic leg oedema, and sleep apnoea. Food-seeking behaviour is common in patients with PWS. Left unchecked and untreated, lack of appetite control can lead to morbid obesity, typically manifesting in early childhood. Therefore improvement in weight control remains the most important goal of any PWS treatment programme.

A study by Brambilla et al. investigated metabolic syndrome in 109 children with PWS aged 2–18 years (50 with obesity and 59 without obesity) and 96 controls with obesity without PWS. 16% of the subjects with obesity and PWS had metabolic syndrome (very close to that observed in the controls with obesity), whereas none of the subjects with PWS without obesity had metabolic syndrome, suggesting that obesity status play a key role in the development of metabolic syndrome.

For treatment and prevention of obesity in PWS, low calorie and well-balanced diets with rigorous supervision and restriction of food access combined with regularly scheduled meals and physical activities are recommended. The treatment of obesity in PWS is difficult and requires a comprehensive multidisciplinary approach with establishment of rigid structures to limit food intake and promote supervised physical activity. Bariatric surgery is not recommended for children with PWS.

The role of pharmacotherapy in PWS is uncertain. No medication has shown long-term effectiveness in controlling appetite. In one study, adult patients with PWS were found to have elevated ghrelin concentrations compared to the reference population, raising the possibility that

Protocol: Liraglutide  
Trial ID: NN8022-4179  
UTN: U1111-1162-7884  
EudraCT no.: 2014-004415-37

CONFIDENTIAL

Date: 16 July 2020  
Version: 5.0  
Status: Final  
Page: 23 of 125

Novo Nordisk

ghrelin may contribute to the food-seeking behaviour observed in these subjects. A 56-week study by de Waele et al. found that octreotide (long-acting somatostatin analogue) significantly decreased fasting ghrelin concentrations, but did not significantly affect weight, behaviour, or appetite in 9 adolescents (10.8–18.9 years) with PWS. Another study found that topiramate (anticonvulsant, one of the two components of the obesity medication Qsymia®) had no significant effect on appetite and body mass index (BMI). In a pilot study in adult patients with PWS and obesity and control patients with obesity, a single dose of 10 µg of the GLP-1 receptor agonist (GLP1-RA) exenatide increased satiety independently of measured appetite hormones, lowered glucose before and during a control meal and, increased insulin secretion rate in both groups. Side effects were absent in PWS. In a recent case report of 6 patients by Fintini et al., the effect of long-term treatment with liraglutide (4 patients, 1.2–1.8 mg/day) or exenatide (2 patients, 20 µg/day) was evaluated in adult PWS patients with T2DM. During the 24 months of treatment, a tendency towards decreased BMI, HbA1c, and waist circumference and a significantly decreased mean glycaemia during continuous glycaemic monitoring was detected, especially during the first 12 months.

As children with PWS often suffer from short stature and excessive body fat, growth hormone (GH) has been used to improve linear growth and body composition. In one study reported by Bakker et al., 8 years of GH treatment of 60 children with PWS completely normalised height standard deviation score (SDS). BMI SDS was significantly lower compared to baseline. Although percent fat SDS improved significantly during the first year of GH treatment, it had returned to baseline level after 8 years of GH treatment. One explanation for this could be, that the gradual increase in percent fat SDS seen over the years during the clinical course of PWS, cannot be fully restrained by GH treatment.

## Liraglutide

Liraglutide is a once-daily glucagon-like peptide-1 (GLP-1) analogue classified as a ‘GLP-1 receptor agonist’, with 97% homology to human GLP-1. Liraglutide has unique therapeutic potential for the treatment of obesity, due to its combined effects not only on body weight but also on glycaemic control and other weight-related comorbidities. Liraglutide regulates appetite by increasing feelings of fullness and satiety, while lowering feelings of hunger and prospective food consumption. Liraglutide is a once-daily GLP-1 analogue, obtained by derivatising GLP-1 with a fatty acid, providing a compound with protracted pharmacokinetic properties suitable for once-daily injection.

Liraglutide at once-daily doses up to 1.8 mg has been approved in approximately 90 countries for the treatment of adults with type 2 diabetes mellitus (T2DM) (under the trade name Victoza®). The moderate dose-dependent weight loss observed in clinical trials with liraglutide in T2DM, together with the reductions in glycosylated haemoglobin A1c (HbA1c) and improvements in beta-cell function and cardiometabolic risk factors such as systolic blood pressure led to investigations into

Protocol: Liraglutide  
Trial ID: NN8022-4179  
UTN: U1111-1162-7884  
EudraCT no.: 2014-004415-37

CONFIDENTIAL

Date: 16 July 2020  
Version: 5.0  
Status: Final  
Page: 24 of 125

Novo Nordisk

its potential therapeutic use for weight management. The liraglutide 3.0 mg daily dose was recently approved in the US as an adjunct to diet and exercise for weight management in adults, under the trade name Saxenda® (approval granted 23 December 2014), followed by Health Canada approval end of February 2015, and in Europe by 23 March 2015.

Four phase 3 clinical trials assessing the effect of liraglutide 3.0 mg on body weight reduction have been completed in adult subjects with obesity or overweight with or without T2DM. In general, a 5–10% mean body weight reduction was observed in subjects treated with liraglutide 3.0 mg in these trials. Detailed results from these trials can be found in the Investigator Brochure or the latest version thereof.

To date, two short-term (5 to 6-week) randomised, controlled trials with liraglutide in paediatric subjects have been completed. In the first trial (NN2211-1800), liraglutide at doses up to 1.8 mg was generally well tolerated in paediatric subjects with T2DM aged 10–17 years. Liraglutide's safety/tolerability and pharmacokinetic profiles in adolescents were similar to those observed in adults with T2DM. In the second trial (NN8022-3967), liraglutide at doses up to 3.0 mg was well tolerated in adolescents with obesity without T2DM (aged 12–17 years); no unexpected safety or tolerability issues were detected. As in adults, liraglutide exposure increased with increasing drug dose. Since no safety/tolerability concerns were raised in the NN8022-3967 trial, a large, long-term trial (NN8022-4180) will investigate the efficacy and safety of liraglutide (doses up to 3.0 mg) for chronic weight management in adolescents with obesity ( $\geq 12$  and  $< 18$  years) and without diabetes type 1.

For an assessment of benefits and risks of the trial, see section [18.1](#), in which a description of preclinical findings includes a dose-dependent delay in sexual maturation in juvenile rats, which was more pronounced in females.

### 3.2 Rationale for the trial

Currently, there are no approved weight management pharmacotherapies for children and adolescents within Europe, and in the US the only medication approved by the FDA for children  $\geq 12$  years of age is orlistat. Obesity is a major cause of morbidity and mortality in PWS. It is challenging to achieve weight loss with diet and physical activity alone due to food-seeking behaviour and lack of appetite control in patients with PWS. Therefore there is an unmet medical need for anti-obesity medication as an adjunct to lifestyle interventions in this patient population.

Protocol: Liraglutide  
Trial ID: NN8022-4179  
UTN: U1111-1162-7884  
EudraCT no.: 2014-004415-37

~~CONFIDENTIAL~~

Date: 16 July 2020  
Version: 5.0  
Status: Final  
Page: 25 of 125

**Novo Nordisk**

## 4 Objectives and endpoints

### 4.1 Objectives

#### Primary objective

To compare the efficacy of liraglutide versus placebo on weight loss in paediatric subjects with obesity and PWS at 16 weeks and versus no treatment at 52 weeks.

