Subjects will be randomised 2:1 to receive liraglutide or liraglutide placebo. Part A has four strata as subjects are stratified according to Tanner stage 2–3 and 4–5 and by presence/absence of dysglycaemia. Part B includes subjects with Tanner below 2 (defined as Tanner stage 1 with or without premature adrenarche) and has two strata for presence/absence of dysglycaemia, see section [11](#).

Dysglycaemia is defined as pre-diabetes with FPG 5.6 – 6.9 mmol/L (both inclusive) (100-125 mg/dL) (both inclusive) and/or HbA1c 5.7 – 6.4 % (both inclusive). The HbA1c and FPG results from V2 must be used.

At least 30% of subjects will be from areas with lifestyle and nutrition comparable to that in the European Union (EU). All subjects and/or their legally acceptable representative (LAR) will undergo counselling for weight loss and must be prescribed a structured programme for diet and physical activity throughout the trial (from randomisation to the end of the trial). Placebo injections will be stopped at week 16, at the end of the double-blind period.

Subjects treated with growth hormone therapy may enter the trial and will have no change in treatment plan with growth hormone from randomisation to the end of the open-label period (subjects on growth hormone will stay on, and subjects off growth hormone will stay off during this period. Adjustments to doses of growth hormone are permitted).

Protocol: Liraglutide  
Trial ID: NN8022-4179  
UTN: U1111-1162-7884  
EudraCT no.: 2014-004415-37

~~CONFIDENTIAL~~

Date: 16 July 2020  
Version: 5.0  
Status: Final  
Page: 30 of 125

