#### 6.4 Discontinuation of trial product criteria

The subject must discontinue trial product if the following applies:

1. Due to a safety concern at the discretion of the investigator
2. Non-compliant with trial procedures at the discretion of the investigator.
3. Pregnancy
4. Intention of becoming pregnant
5. Participation in another clinical trial throughout the trial
6. Included in the trial in violation of the inclusion and/or exclusion criteria
7. Diagnosis of acute pancreatitis (section [8.6.3.3](#) and [8.6.2](#))
8. Diagnosis of medullary thyroid carcinoma
9. Weight loss attempts other than what is agreed with the dietitian as part of the trial intervention
10. If diabetes treatment other than diet, physical activity and metformin addition is initiated.
11. Initiation of treatment that based on the investigator's judgement may cause significant weight change. This should also include treatment with any of the following medications: orlistat, zonisamide, topiramate, lorcaserin, phentermine, bupropion, naltrexone or GLP-1 receptor agonists
12. Inadequate psycho- and/or pharmaco therapeutic treatment of a subject's psychiatric disorder (section [8.5.10.3](#))
13. The subject and/or the subject's LAR refuse referral to a mental health professional (MHP) and it in investigator's opinion, it is unsafe for the subject to continue in the trial (section [8.5.10.3](#))
14. Due to safety reasons if at the recommendation of the external DMC and endorsed by the safety committee.
15. If a subject treated with the individual weight-based starting dose experiences unacceptable intolerance as judged by the investigator, the subject must be discontinued from trial product (Section [8.1.8](#))

See section [8.1.8](#) for how to handle discontinuation of trial product.

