**Table 17–1 Sample size calculations for different scenarios; total number of subjects**

Power	Treatment difference (completers)	SD		
		0.15	0.25	0.35
80%	-0.22	27	63	117
	-0.225	27	60	111
	-0.23	24	57	108
85%	-0.22	30	72	132
	-0.225	30	69	126
	-0.23	27	66	123
90%	-0.22	33	81	156
	-0.225	33	78	147
	-0.23	33	75	141

It seems realistic and conservative to assume a SD of 0.25 and a withdrawal rate of 10% after 16 weeks and 20% after 52 weeks. A withdrawal rate of 10% gives 57 subjects randomised. With this setting, a treatment difference of -0.23 corresponding to approximately a 5-6% decrease in BMI can be detected with a power of 80%. Assuming a withdrawal rate at 20% at week 52 a trial completion of 45 subjects, which is a regulatory requirement, is obtainable.

The distribution of the 57 subjects for randomisation on part A and B and the two treatment groups are shown in the table below.

Protocol: Liraglutide  
 Trial ID: NN8022-4179  
 UTN: U1111-1162-7884  
 EudraCT no.: 2014-004415-37

~~CONFIDENTIAL~~

Date: 16 July 2020  
 Version: 5.0  
 Status: Final  
 Page: 91 of 125

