**17.3 Primary endpoints**

The two co-primary endpoints are:

Protocol: Liraglutide  
Trial ID: NN8022-4179  
UTN: U1111-1162-7884  
EudraCT no.: 2014-004415-37

CONFIDENTIAL

Date: 16 July 2020  
Version: 5.0  
Status: Final  
Page: 92 of 125

Novo Nordisk

- Change from baseline in BMI SDS after 16 weeks of treatment
- Change from baseline in BMI SDS after 52 weeks of treatment

The hypotheses of equality between liraglutide and placebo for each of the two endpoints are tested in a hierarchical manner in the order in which the endpoints are presented. The implication is that liraglutide will only be considered statistically significantly better than placebo at 52 weeks if it is considered statistically significantly better with respect to the first primary endpoint.

The primary analysis will include subjects from all strata, i.e. both from part A and part B (provided that the external DMC recommends that part B will be conducted).

BMI SDS will be summarised using descriptive statistics according to the stratification factor for Tanner stage and stratification factor for glycaemic category. In case there are a very low number of subjects within one glycaemic category, the description may be done according to stratification factor for Tanner stage alone.

The analysis of each of the co-primary endpoints will use the same approach and is described below.

The objective is to show that liraglutide is superior to placebo in obtaining weight loss.

Let  $\mu_{\text{liraglutide}}$  and  $\mu_{\text{placebo}}$  denote mean change in BMI SDS for liraglutide and placebo respectively. The null-hypothesis and the alternative hypothesis are:

$H_0: \mu_{\text{liraglutide}} = \mu_{\text{placebo}}$  against the alternative  $H_A: \mu_{\text{liraglutide}} \neq \mu_{\text{placebo}}$

The null-hypothesis will be rejected on a 5% level if the two-sided 95% confidence interval of the treatment difference  $\mu_{\text{liraglutide}} - \mu_{\text{placebo}}$  excludes 0. If the upper limit is below 0 superiority of liraglutide against placebo can be concluded.

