**Table 5-2 Taxonomy for subjects based on of week 16 and 52 assessments being available or missing**

Assessment at week 16 and 52	On randomised treatment at week 16 and 52	Type description	Type abbreviation
Available	Yes	Available on randomised treatment: Subjects who did not discontinue randomised treatment prematurely with an assessment at week 16 and 52.	AT
	No	Available drop-outs: Subjects who discontinued randomised treatment prematurely but returned to have an assessment at week 16 and 52; also called retrieved drop-outs.	AD
Missing	Yes	Missing on randomised treatment: Subjects who did not discontinue randomised treatment prematurely without an assessment at week 16 and 52.	MT
	No	Missing drop-outs: Subjects who discontinued randomised treatment prematurely and did not return to have an assessment at week 16 and 52; also called non-retrieved drop-outs.	MD

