### 5.3.3 Sensitivity analysis

To investigate the sensitivity of the results of the main analysis of the primary endpoint about the handling of missing data, the following sensitivity analyses will be performed.

An ANCOVA will be performed with imputation of missing values according to the last observation carried forward (LOCF) method. The model will include factors, covariates and interaction term as listed in [Table 5-1](#). The response variable will be the last available measurement of BMI SDS obtained within the 16-week double-blind period of the trial. Data from nominal visits (V10x and V19x) will not be used for this analysis.

Statistical Analysis Plan  
Trial ID: NN8022-4179  
UTN: U1111-1162-7884  
EudraCT No: 2014-004415-37

~~CONFIDENTIAL~~

Date:	14 December 2020	Novo Nordisk
Version:	1.0	
Status:	Final	
Page:	17 of 36	

- The same type of ANCOVA as above will be performed but using an imputation of missing values according to the baseline observation carried forward (BOCF) method. Missing measurements of BMI SDS at 16 weeks will with this method be imputed by the corresponding baseline values. Data from nominal visits (V10x and V19x) will not be used for this analysis.
- The same type of ANCOVA as above will be performed without imputation by only including subjects who completed the 16-week double-blind period. Data from nominal visits (V10x and V19x) will not be used for this analysis.
- A mixed model for repeated measurements (MMRM) will be applied where all post baseline BMI SDS measurements obtained at planned visits during the 16-week double-blind period will enter as the dependent variables, and the factors, covariates and interaction term as listed in [Table 5-1](#) will be included in the model. . All these factors and covariates will be nested under visit, which is technically the same as introducing the corresponding interaction terms in the model. An unstructured covariance matrix for the BMI SDS measurements within subject will be employed. Data from nominal visits (V10x and V19x) will not be used for this analysis.

The sensitivity analyses will be repeated for the week 52 co-primary endpoint.

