The ANCOVA model with LOCF assumes that post treatment discontinuation, the body weight is on average stable in both treatment arms. If the assumption holds, the treatment effect (effectiveness estimand) in each arm and the treatment difference can be estimated from this analysis unbiased. If the withdrawal and the development in both arms are similar, the treatment difference can be estimated from this analysis unbiased. If the development in body weight after treatment discontinuation differs between active and placebo, this analysis might provide an optimistic or over-conservative estimate, depending on the actual circumstances. The analysis is included to be able to compare the results with legacy obesity programs, where this analysis was the main analysis of the primary endpoints.

The ANCOVA model with BOCF assumes that post treatment withdrawn subjects with missing values returns to a body weight in the proximity of their baseline body weight regardless of the timing of withdrawal. This analysis is expected to provide a conservative estimate (effectiveness estimand) of the treatment effect (in each arm). The impact of this assumption on the treatment difference depends on withdrawal pattern over time and development of body weight post withdrawal and reason for withdrawal. The analysis is typically expected to provide a conservative estimate of the treatment difference (effectiveness estimand).

The ANCOVA analysis in completers is expected to give more positive results than the primary analysis. However, this analysis has its own clinical interpretation and will serve as a benchmark and provide an estimate of the efficacy estimand in the population that tolerate the trial product and endure the diet and exercise counselling program.

The MMRM model assumes that withdrawn subjects, had they completed the trial, would not have behaved differently than completing subjects from the same treatment arm with the same baseline characteristics and change in body weight at time of withdrawal. This analysis estimates the treatment difference had all subjects stayed on the randomised treatment (efficacy estimand).

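### In the week-52 sensitivity analyses, data after a prohibited weight-loss drug are dropped for liraglutide children but kept for placebo children; the co-primary analysis treats both arms alike

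*Protocol*

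**What the plan says.** At week 52 the comparator is no treatment: the objective is "weight loss in paediatric subjects with obesity and PWS at 16 weeks and versus no treatment at 52 weeks" (Protocol 4.1). Protocol 5.1 states "Placebo injections will be stopped at week 16, at the end of the double-blind period", and section 11 confirms that only the liraglutide arm has trial product afterwards.

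Protocol 5.3 rules out the named weight-loss drugs and other GLP-1 receptor agonists, without limiting this to one arm or period. The consequence is set in 6.4, item 11: "Initiation of treatment that based on the investigator's judgement may cause significant weight change" requires trial product to be stopped. Under 8.1.8, a child who stops product between V11 and V19 should attend V19x at week 52.

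The main analysis uses V10x and V19x values before anything is imputed, with children analysed as randomised (Protocol 17.2; SAP section 4). Retrieved drop-outs count as available, and missing values are imputed from the available placebo data (SAP Table 5-2 and 5.3.2.2).

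For the sensitivity analyses SAP 5.3.3 says "Data from nominal visits (V10x and V19x) will not be used for this analysis". Protocol 17.3 had this exclusion for LOCF only; SAP 6.2.1 extends it to BOCF, MMRM and completers. Of the MMRM, SAP 5.3.3 says: "This analysis estimates the treatment difference had all subjects stayed on the randomised treatment (efficacy estimand").

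SAP Table 5-2 defines its on-treatment type as "Subjects who did not discontinue randomised treatment prematurely with an assessment at week 16 and 52". SAP Table 4-2 fixes the placebo on-treatment period at weeks 0 to 16. Neither document says what on randomised treatment, or 52-week completer, means for a placebo child after week 16.

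**The concern.** The rule that removes a child's later data from the sensitivity analyses runs through product discontinuation. After week 16 that route exists in one arm only, so the same event leads to different data handling depending on allocation.

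These analyses are there to test how far the week-52 result depends on missing-data assumptions. The MMRM and completer analyses are also meant to speak to an efficacy estimand. If placebo children on another weight-loss drug stay in as untreated while their liraglutide counterparts drop out, those analyses do not answer the question set for them, and the reader cannot tell by how much. In the co-primary analysis a smaller question remains: drug-treated placebo children would be counted as no treatment and would also feed the imputation.

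**Working it through.** **1. The plan's own figure.** Protocol 17.1 and 17.3 give a two-sided 5% test ("The null-hypothesis will be rejected on a 5% level if the two-sided 95% confidence interval"), SD 0.25, 2:1 allocation and 10% withdrawal at week 16, and say that "a treatment difference of -0.23 corresponding to approximately a 5-6% decrease in BMI can be detected with a power of 80" per cent.
- Corrected difference: 0.9 × 0.23 = 0.207.
- Corrected SD: √(0.25² + (2/3)(0.1)(0.9)(0.23²)) = 0.2563.
- A two-sample t-test with 38 and 19 children gives 80.6% power, so N = 57 is reproduced. The same method matches all 27 cells of Table 17-1.

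This rests on week 16, when both arms have product and item 11 applies to both. N is not affected by this point.

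**2. The same event in each arm, drug started at week 30, say.**

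| | Liraglutide child | Placebo child |
|---|---|---|
| Product to stop (6.4, item 11) | Yes | None since week 16 |
| Week-52 visit | V19x | V19 |
| Co-primary analysis | Value kept | Value kept |
| LOCF | Week-52 value excluded; earlier value carried forward | V19 used |
| BOCF | Set to baseline | V19 used |
| Completers | Dropped | Kept |
| MMRM | Earlier visits only | V19 used |

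**3. Assumptions for the size.** The documents give no starting rate, no effect for another drug and no week-52 effect for liraglutide. I take D = 0.23 (the week-16 planning value), a share f of 5%, 10% or 20% starting a drug, and a drug effect of e × D with e = 0.5 or 1. For BOCF the mean untreated change is set to zero.

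**4. Sensitivity analyses.** The share f applies to both arms, with no other missing data.
- V19x kept in both arms, or BOCF applied to starters in both arms: D(1 − f).
- BOCF as planned: D(1 − f) − f·e·D.
- Completers as planned: D(1 − f·e). Starters dropped in both arms: D = 0.23.

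| f | e | BOCF, both arms alike | BOCF as planned | Completers as planned |
|---|---|---|---|---|
| 5% | 0.5 | 0.2185 | 0.213 | 0.224 |
| 5% | 1 | 0.2185 | 0.207 | 0.2185 |
| 10% | 0.5 | 0.207 | 0.1955 | 0.2185 |
| 10% | 1 | 0.207 | 0.184 | 0.207 |
| 20% | 0.5 | 0.184 | 0.161 | 0.207 |
| 20% | 1 | 0.184 | 0.138 | 0.184 |

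The loss from unequal handling is f·e·D in both analyses. It runs from 0.05 × 0.5 × 0.23 = 0.006 to 0.20 × 1 × 0.23 = 0.046.

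**5. In children.** With 20% withdrawal, 19 × 0.8 ≈ 15 placebo children have week-52 data. One, two or three starters at full effect move the placebo mean by k × 0.23/15 = 0.015, 0.031 or 0.046, which is 7%, 13% or 20% of 0.23.

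**6. Co-primary analysis.** Here 20% withdraw and only placebo children start drugs. The liraglutide mean benefit is 0.8D + 0.2·f·e·D and the placebo mean is f·e·D, so the contrast is 0.8·D·(1 − f·e). It falls from 0.184 to between 0.179 (f = 5%, e = 0.5) and 0.147 (f = 20%, e = 1). Adding (1/3)·f(1 − f)(eD)² to the corrected variance, power with 57 children falls from 69% to between 67% and 49%. If the week-52 difference were 0.30, it falls from 88% to between 86% and 68%. This is dilution of the comparator under one rule for both arms.

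**The case against.** The case against acting is substantial.

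- The analysis that decides the trial is not affected by the asymmetry. It follows an intention-to-treat principle and keeps measured values in both arms. Only four supportive analyses are involved.
- The drugs are prohibited in both arms (5.3). Starting one is a protocol deviation to be documented (8.1 and 19), and single observations can be considered for exclusion at the data review before lock (SAP section 4).
- Starters may be few. Protocol 3.2 reports no approved paediatric weight-management drug in Europe and only orlistat, from age 12, in the US. Section 17.1 relies on the lack of other options.
- The full 0.23 is generous. Section 3.1 reports no significant effect of topiramate on BMI, and 18.1 reports less weight loss with orlistat than with liraglutide in adults. Section 17.1 also expects a larger difference at week 52 than at week 16, which would shrink the percentages above.

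All of this stands, and it limits the size of the point. It does not supply the missing rule. A prohibition does not say how a value is analysed once it has been breached. Exclusion at data review is meant to be restrictive, and sites know the allocation from V10, so a case-by-case decision is weaker than a written rule.

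**Conclusion.** The point holds for the four week-52 sensitivity analyses. Starting a drug under 6.4, item 11 removes the week-52 value in one arm and has no effect on the data in the other. The MMRM therefore does not estimate its stated estimand in the placebo arm. Under the assumptions shown, the planned completer and BOCF differences are 0.006 to 0.046 SDS smaller than with equal handling. The true size depends on an unknown and possibly small number of starters among about 15 observed placebo children.

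Three stronger readings are tempting, and the documents do not support them:
- That the week-52 co-primary contrast is handled differently by arm. It is not: V19x is used there and retrieved drop-outs count as available. What remains is a no-treatment comparator that may include some drug-treated children.
- That untreated placebo children are likely to start another drug. No passage gives a rate, and sections 3.2 and 17.1 point the other way.
- That liraglutide could gain a false claim. Under these assumptions the shift runs against it.

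This is a modest gap that is cheap to close.

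**What to change.** In SAP Table 5-2 and 5.3.3, define on randomised treatment and 52-week completer for placebo children after week 16 as not having started a drug listed in Protocol 6.4, item 11. In the four week-52 sensitivity analyses, exclude placebo values after the recorded start date, as already happens for liraglutide through V19x. Leave the primary analysis unchanged, and report the number of starters by arm.

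Reconcile the flow chart, which has no concomitant medication mark at V10x or V19x, with Protocol 8.3.3, which asks for changes to be recorded at each visit. V19x weights enter the primary analysis, so drug use in those children should be known.

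I would not rerun the primary imputation with drug-free placebo donors only. That selects donors on a post-randomisation event. The full model in SAP Table 5-3 has 11 coefficients (intercept 1, sex 1, region 3, Tanner 2, glycaemic category 1, interaction 2, BMI SDS 1). With 15 donors less three starters, 12 − 11 = 1 residual degree of freedom would remain.

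The cost is SAP wording and one count by arm, using medication data already collected for placebo children. The downside is that a few placebo values may be lost from the sensitivity analyses. N is unaffected.
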